## **10. Study Procedures**

[figure not shown]
The section below describes the study procedures that the subject will undergo during the clinical study.

### **10.1 Schedule of Events**

Subjects will participate in a minimum of 8 planned study visits as presented in **Figure 3** or approximately 3 weeks to 6 months of device wear. If a subject is repeating participation in the study, the subject will participate in another minimum 8 planned visits. Refer to **Table 4** for additional visit details.

If subject ends the study early (i.e. before their last scheduled visit), all requirements that apply to the final visit should be completed if possible.

**Figure 3. Visit Schedule**

The study is comprised of a run-in period of approximately 1 week to 3 months and a study period of approximately 10 days.

Prior to study start, Investigator or authorized designee must obtain written informed consent from the patient before any clinical study related activity (including screening) takes place and document informed consent process in the medical chart of the patient (refer to **Section 10.11 Subject Consent**).

Study staff will discuss with the participant the visit schedule and will make arrangements with the subjects for the contacts at investigational center and sponsor. Participants who are not compliant with the arranged contacts, which may impact patient's safety, may be discontinued at the discretion of the investigator.

Subjects will be using the Klue Health app and Apple Watch. The subject must wear the Apple watch on the wrist of the hand used for eating for the duration of the study.

Subjects will also be using the [REDACTED]

### **Run-in Period (approximately 1 week to 3 months in total after starting devices):**

The run-in period is intended to allow subjects to become familiar with the new study devices, while using the same insulin they will be using during the study period.

For the duration of the at-home run-in period and the at-home study period (baseline meal challenges, see details below), study subjects will be using the study pump with SmartGuard Auto Mode turned ON (after warm-up period).

For the run-in period, The Klue Health app will be configured in monitoring-only mode. The subject must wear the Apple watch on the wrist of the hand used for eating.

### **Study Period – At-Home: Baseline Meal Challenge**

Study subjects will undergo a 5-day meal challenge at specific meal(s) on each day.

#### **5 days of baseline meal challenges at home:**

- Day 1: long meal with low carb count (lunch) and large meal with low carb count (dinner)
- Day 2: small meal with high carb count (lunch)
- Day 3: large drink with no carbs (breakfast) and typical meal size with medium carb count (dinner)

*Medtronic Business Restricted*

- Day 4: long meal with high carbs (lunch)
- Day 5: large drink with high carbs (breakfast) and typical meal size with low carb count (lunch)

For the baseline meal challenges, study subjects will be asked by investigational center staff to eat a pre-defined meal, while bolusing using the pump's bolus calculator (manually announcing the meals) and logging the challenge meals in the FoodPrint app. For all other meals, subjects can consume their usual meals, but meals do not need to be logged in FoodPrint.

The Klue Health app should remain configured in monitoring-only mode during this time. The subject must wear the Apple watch on the wrist of the hand used for eating.

#### **Study Period – 5 days (4 nights) In-Clinic:**

After the run-in period and completion of the 5-day at-home study period with baseline meal challenges, study subjects will check into the clinic for a 5-day (4 nights) intervention.

Study subjects will be asked by investigational center staff to consume meals of the same size and content they consumed for the meal challenges during the baseline meal challenge (at-home study period). For example: If a large sized dinner meal with low carbohydrate content was consumed at 5 pm on Day 1 during the baseline meal challenge, that same dinner meal should be consumed at approximately the same time on Day 1 of the in-clinic study period. Subjects will be asked by investigational center staff to check BG at the start of the meal, as well as 2 hours and 4 hours after the start of the meal and provide correction as necessary. All meals consumed during the in-clinic study period should be logged in the FoodPrint app.

Subjects will be instructed by investigational center staff to not use the pump's meal bolus calculator (no manual meal announcements) for the duration of the intervention.

Scheduled meal challenges during the study period (mirror baseline meal challenge):

- Day 1: long meal with low carb count (lunch) and large meal with low carb count (dinner)
- Day 2: small meal with high carb count (lunch)
- Day 3: large drink with no carbs (breakfast) and typical meal size with medium carb count (dinner)
- Day 4: long meal with high carbs (lunch)
- Day 5: large drink with high carb (breakfast) and typical meal size with low carb count (lunch)

On Day 5 of the in-clinic meal challenge, a subject may be asked to repeat a specific meal challenge which may require the subject to participate for an additional day.

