# CIP339 Clinical Investigation Plan

D00456959

Version F

Page 46 of 93

Medtronic

Visit Window	Run-In Period						Study Period					End of Study	
	Visit 1 (Office)	Visit 2 (Office )	Visit 3 (Phone)	Visit 4 (Phone)	Visit 5 (Phone)	Visit 6 (Phone)	Visit 7 (Office)						
							Day 1	Day 2	Day 3	Day 4	Day 5		
Train subject on diabetes management principles, such as the treatment of hyperglycemia and hypoglycemia. In addition, there will be training regarding the need to have access to oral glucose and glucagon in case of hypoglycemia.		X											
Train subject to have back up plan in place (e.g. insulin pen or syringe) in the event they are asked to revert back to their own therapy during the study or experience study pump issues (i.e. infusion set occlusion with high glucose).		X											
Train subjects on the use of the study meter to self-monitor blood glucose (SMBG) as needed for standard of care and to make treatment decisions. Refer to user guide. 
 
If sensor glucose readings are not aligned with symptoms (e.g., if a study subject is feeling low while the sensor glucose reading is not low), use the meter to confirm blood glucose. If sensor glucose readings continue to be different from symptoms, call the study doctor
 
		X											
Train subjects on the use of ketone meter. Instruct subjects that blood ketone testing is required every time BG is greater than 300 mg/dL (16.7mmol/L), as measured by the study meter. In the event the blood ketone meter is not used to collect ketone values, urine ketones should be measured and reported.		X											

Medtronic Business Restricted

CONFIDENTIAL

056-F275, vC Clinical Investigation Plan Template

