# CIP339 Clinical Investigation Plan

D00456959

Version F

Page 48 of 93

Medtronic

Visit Window	Run-In Period						Study Period					End of Study	
	Visit 1 (Office)	Visit 2 (Office )	Visit 3 (Phone)	Visit 4 (Phone)	Visit 5 (Phone)	Visit 6 (Phone)	Visit 7 (Office)						
							Day 1	Day 2	Day 3	Day 4	Day 5		
Train and start study subjects on [REDACTED] upon product availability. Refer to study material.	Enrollment /Screening	Day -6 (-90 days) Start Run-In	Day -3 (-90, +2 days)	Day -1 (-1, +2 days)	Day 0 (-2, +1 days)	Day 6 (-2 days)	Day 7 (+10 days)						
Train and start study subjects on SmartGuard (Auto Mode) feature. 
 
Use the default SmartGuard target of 100mg/dL.
 
Ensure that the auto correction feature is turned ON and remains ON throughout the course of the study.
 
Instruct subjects that they should not assume that Auto Mode is able to prevent all hypoglycemia or all hyperglycemia including diabetic ketoacidosis
 
While the SmartGuard feature is active, use the temp target feature if medication containing paracetamol or acetaminophen has been taken recently. Check the label of any medication to confirm whether paracetamol or acetaminophen is an active ingredient.
 
 Auto Mode should be switched OFF in the study pump or that subjects switch to manual injections if: 
 
Hospital admission is needed for any reason
 
Glucose is persistently elevated (i.e., above 300 mg/dL [16.7 mmol/L])
 
There is an illness that prevents ingestion of fluids due to nausea and vomiting
 
		X (if available)	X (if available)	X (if available)	X (if available)	X (if available)	X (if available)	X (if available)	X (if available)	X (if available)			

Medtronic Business Restricted

CONFIDENTIAL

056-F275, vC Clinical Investigation Plan Template

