**Table 5. Risks, Prevention and Mitigation**

Risks with Infusion Sets	Prevention and Mitigation

Risks with infusion sets may include:
 

• Localized infection

• Skin irritation/redness

• Bruising

• Discomfort/pain

• Bleeding

• Irritation

• Rash

• Hyperglycemia secondary to infusion set occlusion or infusion site failure including DKA

• Hyperglycemia secondary to site falling off including DKA

• Anxiety associated with insertion

	
Prevention and mitigation include:
 

• Follow the provided user guides for insertions and care of infusion sets.

• If an infusion site becomes irritated or inflamed, the infusion set will be removed and another placed in a new location.

• In case of hyperglycemia secondary to infusion set occlusion, remove current infusion set and replace with new infusion set and give correction insulin if needed with syringe.

• Follow the provided user guides for insulin pump management.

• Train prior to study device use on appropriate device use and diabetes management principles and instruct to call investigator with problems.

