## 12.2 Reporting of Adverse Events and Device Deficiencies

The investigator or designee will record all AEs and DDs while the subject is enrolled in the clinical study.

Each AE needs to be assessed for its device or procedure relatedness. A device related AE is associated with the use of the study device (e.g. infection of sensor site or infusion set occlusion resulting in DKA). A procedure related AE is associated with testing related to the study procedures specified in the CIP.

Examples of device or procedure related AEs include:

- **Device** related: insertion site infection
- Serious adverse **device effect**: cellulitis at device insertion site requiring hospitalization
- **Procedure** related AE: meal challenge procedure

Subjects participating in the study have diabetes and are expected to experience hypoglycemia and or hyperglycemia. These normal events are not expected to be reported to sponsor on an AE eCRF as this is not considered an untoward event, but rather an expected occurrence. Any glycemic excursion that meets the protocol definition of Severe Hypoglycemia, Severe Hyperglycemia or DKA is considered an untoward event and a worsening from the subject's baseline and would be reported to sponsor on an AE eCRF.

Baseline medical conditions should only be reported to sponsor on an AE eCRF, if there is a worsening from the subject's baseline. For example, a subject previously diagnosed with Asthma is hospitalized for severe asthma attack would be a reportable event.

Adverse events will be documented in the subject source file and reported to sponsor on an eCRF. The investigational center is responsible for documentation of AEs including obtaining source documents related to the event, such as emergency medical technician/paramedic reports, hospital records (admission summary; lab results, test results, discharge summary) or device uploads to support the event. Source documents will be reviewed to determine if additional AEs have occurred and require reporting.

Adverse events that have not resolved at the time of the subject's discontinuation or completion of the study should have an "outcome" of Not Recovered/Not Resolved at study end in subject source and on an eCRF. The investigator should ensure that subject is aware of any follow-up or additional treatment that is required for any ongoing AE at end of study participation; however, there will be no eCRF entry for the ongoing follow-up.

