7.9.1 Primary Endpoints

- Post-prandial Time in range (% of SG within 70-180 mg/dl) At-Home and In-Clinic Period will be summarized, respectively.

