7.9.3 Other Endpoints

All measurements performed by Study Period (At-Home and In-Clinic period).

- Post-prandial Time in different ranges (% of SG): SG <54, 70 mg/dL, SG > 180, 250 mg/dL
- Change in post-prandial % of time in euglycemia (70-180 mg/dL) for meal challenges (intervention versus baseline)
- Change in post-prandial % of time in different ranges (% of SG): SG <54, 70 mg/dL, SG > 180, 250 mg/dL for meal challenges (intervention versus baseline)
- 24 hour Time in range (% of SG within 70-180 mg/dl)
- 24 hour Time in different ranges (% of SG): SG <54, 70 mg/dL, SG > 180, 250 mg/dL
- Number of Events, Area Under Curve (AUC) and Time in the hyperglycemic range: sensor glucose (SG) > 180, 250 mg/dL
- Number of Events, AUC and Time in the hypoglycemic range: SG < 54 and 70 mg/dL

- Time spent in Auto Mode versus time spent in Manual Mode
- Change of Total Daily Dose (TDD) of insulin from baseline to EOS Period
- Change in BG values during meal challenge (BG prior and BG 2 hours after meal)
- Insulin delivery at postprandial: Total unit of insulin in first 15 minutes, 60 minutes, 120 minutes, and 240 minutes postprandial
- Subgroup analysis by type of meals
- Between period analyses of all above (At-Home vs. In-Clinic)

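### The scheduled 2 h and 4 h check-and-correct step exists only in the clinic, and the SAP does not separate manual correction from gesture dosing

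*Protocol*

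**What the plan says.** **In clinic.** Protocol 10.1 (in-clinic study period) has subjects repeat the home challenge meals without manual announcement. They check BG at the start of the meal and "2 hours and 4 hours after the start of the meal and provide correction as necessary". No threshold, type of correction or recording rule is given there.

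**At home.** Under the baseline meal challenges in 10.1, subjects "eat a pre-defined meal, while bolusing using the pump's bolus calculator (manually announcing the meals) and logging the challenge meals in the FoodPrint app". Neither that text, nor 10.3.1.2, nor Table 4 schedules a post-meal BG check or a correction.

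**Both periods.** Table 4 tells staff to "Ensure that the auto correction feature is turned ON and remains ON throughout the course of the study", and trains subjects to use the meter "as needed for standard of care and to make treatment decisions".

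**Endpoints.** SAP 7.9.1 says that post-prandial TIR "At-Home and In-Clinic Period will be summarized, respectively", without giving the length of the post-prandial window. SAP 7.9.3 adds:
- change in post-prandial TIR and in time in other ranges, intervention versus baseline;
- 24-hour TIR and change in total daily dose;
- BG change from before the meal to 2 h;
- insulin as "Total unit of insulin in first 15 minutes, 60 minutes, 120 minutes, and 240 minutes postprandial";
- between-period analyses of all of these.

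SAP 7.4 includes all available data.

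**Recording.** Protocol 12.2 says of ordinary hypo- and hyperglycemia: "These normal events are not expected to be reported to sponsor on an AE eCRF". FoodPrint (7.1.2.7) is used in this study for meals and activity. Table 4 has no row for post-meal BG or corrections. Table 5 mentions a non-pump route, "give correction insulin if needed with syringe", for infusion-set occlusion.

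**The concern.** The plan matches the two periods on meal size, content and approximate time, but not on scheduled post-meal management. If an in-clinic meal is under-dosed or undetected and is corrected at 2 h, later glucose readings and later insulin reflect the correction as well as the automated dosing. The same applies when carbohydrate is given after an over-dosed meal. The SAP has no step that flags, censors or reports these data separately, so a reader of the results could not tell the two apart.

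The need for a manual correction is also a direct sign of how well gesture dosing covered a meal, and no endpoint counts it. That matters in a study whose stated purpose is the safety of gesture dosing and whose data feed product development. Severe hypoglycemia and DKA are unlikely to fill the gap while subjects are under constant surveillance in the clinic.

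**Working it through.** The study is unpowered and states no effect size, so there is no plan figure to reproduce. The check is which endpoints a scheduled correction can reach, and how much of a window it could touch.

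**1. Inputs from the documents.** Scheduled in-clinic checks fall at t = 2 h and t = 4 h. Insulin windows end at 15, 60, 120 and 240 min. The BG endpoint is read at 2 h. Challenge meals per period in 10.1 are 2 + 1 + 2 + 1 + 2 = 8, so 16 completers give 16 × 8 = 128 per period before repeats. (Section 10.3.2.1.4 also lists a Day 4 breakfast in the clinic that the 10.1 list does not contain. It is not counted here.)

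**2. Assumptions, because the documents are silent.** W = post-prandial window in hours; L = lag before a correction acts, 0 to 0.5 h; f = share of in-clinic challenge meals corrected at 2 h; c = share of post-correction readings moved into range.

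**3. Share of the window after a correction** = max(0, W − t − L) / W. Each cell runs from L = 0 to L = 0.5 h.

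| W | after the 2 h check | after the 4 h check |
|---|---|---|
| 2 h | 0% | 0% |
| 3 h | 33% to 17% | 0% |
| 4 h | 50% to 38% | 0% |
| 5 h | 60% to 50% | 20% to 10% |
| 6 h | 67% to 58% | 33% to 25% |

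**4. Endpoint by endpoint, for the same meal's scheduled correction.**
- Insulin at 15, 60 and 120 min: precedes the 2 h correction, not affected.
- BG at 2 h: this is the reading that prompts the correction, not affected.
- Insulin to 240 min: includes pump insulin given at 2 h. A correction after the 4 h check falls at or beyond the end of the window.
- Post-prandial TIR and its change: affected by the 2 h correction only if W > 2 h, and by the 4 h correction only if W > 4 h.
- 24-hour TIR and total daily dose: open to both.

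**5. Illustrative shift in in-clinic post-prandial TIR**, W = 4 h: 100 × f × c × (4 − 2 − L) / 4.
- f = 10%, c = 10%: L = 0.25 gives 100 × 0.1 × 0.1 × 0.4375 = 0.4 points; L = 0.5 also rounds to 0.4.
- f = 25%, c = 25%: 2.7 points (L = 0.25) to 2.3 points (L = 0.5).
- f = 50%, c = 50%: 10.9 points (L = 0.25) to 9.4 points (L = 0.5).

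The formula counts only readings moved into range and subtracts nothing for corrections made at home. It shows scale and does not estimate bias.

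**The case against.** Much of the case on the other side stands.

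- **The primary endpoint may be untouched.** With a 2 h window, no sensor reading in it follows the meal's first scheduled correction. A reader might infer that both corrections contaminate post-prandial TIR. The documents do not support that: the window is undefined, and the 4 h correction cannot reach a 4 h window or the 240-minute insulin total.
- **Home meals are not free of correction.** Auto-correction runs in both periods, subjects bolus with the calculator, and meter-based treatment decisions are allowed. The difference is scheduled versus unscheduled correction.
- **Direction is not shown.** It is tempting to say that correction makes both kinds of dosing failure look better. Improvement is the natural expectation, but no threshold or type of correction is stated. Correction insulin could add time below range, and carbohydrate could add time above 180 mg/dL.
- **Some of the data exist.** Pump data upload automatically (10.9.4), and SAP 7.9.3 counts sensor excursions by period, so keeping ordinary excursions off the AE form does not hide them. The eCRFs and worksheets (16.4.1, 16.4.2) are separate documents and may already hold a correction field.
- **The stakes are modest.** The primary endpoint is a summary for each period with no success criterion. The contrasts are among the other endpoints of an unpowered feasibility study, and they also mix home with clinic and period order. SAP 7.9 already permits extra analyses.

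Three things survive this. The 240-minute insulin, 24-hour TIR and total daily dose remain mixed whatever window is chosen. The permission for further analyses cannot recover syringe doses or rescue carbohydrate that were never recorded. And because the pump treats a micro-meal announcement like a manual one (7.1.1.1), separating automated from manual insulin needs a stated rule.

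**Conclusion.** The concern holds in a limited form. Scheduled check-and-correct is specified for the clinic only, and the SAP does not separate what follows a correction. As written, the 240-minute insulin total, 24-hour TIR, total daily dose and their between-period comparisons can mix manual correction with gesture dosing. Post-prandial TIR and its change join them only if the window exceeds 2 h. Meals that needed a manual correction are not counted in any stated endpoint.

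Size and direction are unknown. The 0.4 to 11 point range rests wholly on an assumed 4 h window and on assumed correction rates, effects and lags. It should not be read as evidence that in-clinic TIR is inflated. This is an inexpensive improvement that should be made. It does not invalidate a descriptive feasibility study.

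**What to change.** Leave care as it is and change the recording and analysis:

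1. State the post-prandial window in SAP 7.9.1.
2. Record the time, type, amount and route of every non-automatic correction for each challenge meal, in both periods, if the eCRFs do not already do so. This has to happen at the time, because carbohydrate and syringe insulin may not be recoverable later.
3. Report post-prandial TIR and time below range for 0–2 h from meal start beside the full-window result.
4. Report the number and percent of challenge meals with a non-automatic correction, by period and app release.
5. Split the 240-minute insulin into automated delivery and manual correction, with the rule for the split written down.

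The sponsor should also reconcile the at-home and in-clinic post-meal procedures in Protocol 10.1. One reason is that the 2 h BG endpoint is listed for both periods but the check is scheduled in only one. No clinical rule is proposed here.

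The cost is one log field per challenge meal and a few tables. The 0–2 h summary uses fewer readings per meal and will be somewhat noisier. Visits and subject numbers do not change.

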## 10.2 Study Start and Run-In Phase

### 10.2.1 Visit 1: Consent and Screening

The investigational center staff will:

- Obtain written informed consent
- Determine if subject meets eligibility criteria (**Sections 9.3 and 9.4**)
- Collect demographic information
- Review subject's medical history
- Measure/Collect height and weight

### 10.2.2 Visit 2: Start Run-In (Office), Day -6 (window of -90 days)

The investigational center staff will:

- Dispense study devices
- Start Apple Watch with Klue Health app in monitoring mode
- Train subject on meal challenges and how to log meals/activities in FoodPrint
- Provide pump training and CGM training and start on pump system including MiniMed Clinical app
- Complete baseline subject questionnaire
- Ask subject about adverse events or device deficiencies

### 10.2.3 Visit 3: Phone, Day -3 (window of -90, +2 days)

The investigational center staff will:

- Train subject and have subject activate SmartGuard Auto Mode feature
- Remind subject to wear Apple watch on dominant hand used for eating
- Ask subject about adverse events or device deficiencies

### 10.2.4 Visit 4: Phone, Day -1 (window of -1, +2 days and may be combined with Visit 5)

The investigational center staff will:

- Check in with subject to see how pump/CGM wear is going
- Remind subject to wear Apple watch on dominant hand used for eating
- Ask subject about adverse events or device deficiencies

